### 3.10.2 Off-Study Criteria

- Completion of study follow-up period
- Subject requests to be withdrawn from study
- Subject is lost to follow-up
- Death
- Study is cancelled for any reason

## 4 CONCOMITANT MEDICATIONS/MEASURES

Medications or vaccinations specifically prohibited in the exclusion criteria are not allowed during the ongoing trial. If there is a clinical indication for one of these or other medications or vaccinations specifically prohibited during the trial, discontinuation from trial therapy or vaccination may be required. The investigator should discuss any questions regarding this with the Merck Clinical team. The final decision on any supportive therapy or vaccination rests with the investigator and/or the subject's primary physician.

### 4.1 ACCEPTABLE MEDICATIONS

All treatments that the investigator considers necessary for a subject's welfare may be administered at the discretion of the investigator in keeping with the community standards of medical care. All concomitant medication will be recorded on the case report form (CRF) including all prescription, over-the-counter (OTC), herbal supplements, and IV medications and fluids. If changes occur during the trial period, documentation of drug dosage, frequency, route, and date may also be included on the CRF.

All concomitant medications received within 28 days before the first dose of trial treatment and until 30 days after the last dose of trial treatment or until start of next treatment, whichever occurs first, should be recorded. Concomitant medications administered after 30 days after the last dose of trial treatment should also be recorded for SAEs and ECIs (Section [7](#)).

### 4.2 PROHIBITED MEDICATIONS

Patients are prohibited from receiving the following therapies during the Screening and Treatment Phase (including retreatment for post-complete response relapse) of this trial:

- Antineoplastic systemic chemotherapy or biological therapy
- Immunotherapy not specified in this protocol
- Chemotherapy not specified in this protocol
- Investigational agents other than pembrolizumab
- Radiation therapy
  - **NOTE:** Radiation therapy to a symptomatic solitary lesion or to the brain may be allowed at the investigator's discretion.
- Live vaccines within 30 days prior to the first dose of trial treatment and while participating in the trial. Examples of live vaccines include, but are not limited to, the following: measles, mumps, rubella, varicella/zoster, yellow fever, rabies, BCG, and typhoid vaccine.
- Systemic glucocorticoids for any purpose other than to modulate symptoms from an event of clinical interest of suspected immunologic etiology are generally not allowed. For subjects who are on stable doses of steroids (i.e.,  $\leq 10$  mg/day of dexamethasone or

equivalent) at study entry, the investigator should try to taper/discontinue dosing after initiation of therapy, if appropriate. Other exceptions include the use of physiologic doses of corticosteroids and steroid use for acute issues (e.g., for up to 2 weeks unless otherwise felt to be clinically necessary in the opinion of the PI to continue for longer) after consultation with the PI.

Patients who, in the assessment by the investigator, require the use of any of the aforementioned treatments for clinical management should be removed from the trial. Patients may receive other medications that the investigator deems to be medically necessary.

The Exclusion Criteria describes other medications which are prohibited in this trial.

There are no prohibited therapies during the Post-Treatment Follow-up Phase.

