Another research priority is to identify potential biomarkers in the peripheral blood and CSF that correlate with response or toxicity. A recent study demonstrated that PD-1 inhibitors result in an increase in the number of CD8+Ki-67+PD-1+ effector T-cells in the peripheral blood shortly after initiation of therapy in patients with lung cancer. We will use multi-parameter flow cytometry for T-cell and NK-cell subsets and monitor the peripheral blood for an early host adaptive immune response (6 weeks), a “rebound effect” (18 weeks), at 1 years, and 2 years. In addition, we will assess the host immune response at the time of disease progression. In the case of patients with PCNSL, these tests will also be performed longitudinally in the CSF and correlated with response. Tissue biopsy specimens and peripheral blood samples obtained while on pembrolizumab therapy may identify other potential biomarkers that predict response and/or help elucidate the mechanisms of treatment resistance at the cellular level.

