## 2.1.2 Exclusion Criteria

2.1.2.1 Patients with DLBCL who best fit the criteria of EBV+ DLBCL, NOS are not eligible

2.1.2.2 Current or prior anti-cancer treatment prior to the first dose of pembrolizumab as defined below:

- Chemotherapy, targeted small molecule therapy, or other anti-cancer treatment not otherwise specified below within 2 weeks
- Radiation therapy within 2 weeks
- Anti-cancer monoclonal antibody (mAb) treatment within 4 weeks

- Use of an investigational agent (e.g., biologic, drug, or other) within 4 weeks
- Allogeneic stem cell transplant within 100 days
- Prior therapy with an anti-PD-1, anti-PD-L1, or anti-PD-L2 agent at any time

2.1.2.3 No current use of systemic corticosteroids at physiologic doses  $> 10$  mg/day of dexamethasone or equivalent are permitted. Patients receiving current systemic steroids must be on a stable steroid dose (i.e.,  $\le 10$  mg/day of dexamethasone or equivalent at the same dose for at least 7 days). Patients who recently discontinued systemic steroids must have completed them at least 7 days prior to entry.

2.1.2.4 Uncontrolled intercurrent illness including, but not limited to the following that may limit interpretation of results or that could increase risk to the patient at the discretion of the investigator:

- Active autoimmune disease that has required systemic treatment in the past 2 years (i.e., with use of disease modifying agents, corticosteroids or immunosuppressive drugs). **NOTE:** Replacement therapy (e.g., thyroxine, insulin, or physiologic corticosteroid replacement therapy for adrenal or pituitary insufficiency, etc.) is not considered a form of systemic treatment.
- History of (non-infectious) pneumonitis that required steroids, evidence of interstitial lung disease or active, non-infectious pneumonitis.
- Clinically significant history of liver disease, including viral or other hepatitis, current alcohol abuse, or cirrhosis; as well as active infection with HBV or HCV:
  - Patients with occult or prior HBV infection (defined as positive total hepatitis B core antibody [HBcAb] and negative HBsAg) may be included if HBV DNA is undetectable.
  - Subjects who are positive for HCV antibody must be negative for HCV by polymerase chain reaction (PCR) to be eligible for study participation.
- Uncontrolled and/or symptomatic thyroid disease
- Active graft-vs-host disease (GVHD) requiring treatment or any history of  $\ge$  grade II acute GVHD
- Seizure activity within the past 4 weeks

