### 3.3.2 Immune-Related Adverse Events

#### General Instructions:

1. Corticosteroid taper should be initiated upon AE improving to Grade 1 or less and continue to taper over at least 4 weeks.
2. For situations where pembrolizumab has been withheld, pembrolizumab can be resumed after AE has been reduced to Grade 1 or 0 and corticosteroid has been tapered. Pembrolizumab should be permanently discontinued if AE does not resolve within 12 weeks of last dose or corticosteroids cannot be reduced to  $\leq 10$  mg prednisone or equivalent per day within 12 weeks.
3. For severe and life-threatening irAEs, IV corticosteroid should be initiated first followed by oral steroid. Other immunosuppressive treatment should be initiated if irAEs cannot be controlled by corticosteroids.

Immune-related AEs	Toxicity grade or conditions (CTCAEv4.0)	Action taken to pembrolizumab	irAE management with corticosteroid and/or other therapies	Monitor and follow-up
Pneumonitis	Grade 2	Withhold	

• Administer corticosteroids (initial dose of 1-2 mg/kg prednisone or equivalent) followed by taper

	

• Monitor participants for signs and symptoms of pneumonitis

• Evaluate participants with suspected pneumonitis with radiographic imaging and initiate corticosteroid treatment

• Add prophylactic antibiotics for opportunistic infections

	Grade 3 or 4, or recurrent Grade 2	Permanently discontinue		
Diarrhea/ Colitis	Grade 2 or 3	Withhold	

• Administer corticosteroids (initial dose of 1-2 mg/kg prednisone or equivalent) followed by taper

	

• Monitor participants for signs and symptoms of enterocolitis (ie, diarrhea, abdominal pain, blood or mucus in stool with or without fever) and of bowel perforation (ie, peritoneal signs and ileus).

• Participants with <math>\geq</math> Grade 2 diarrhea suspecting colitis should consider GI consultation and performing endoscopy to rule out colitis.

• Participants with diarrhea/colitis should be advised to drink liberal quantities of clear fluids. If sufficient oral fluid intake is not feasible, fluid and electrolytes should be substituted via IV infusion.

	Grade 4	Permanently discontinue		

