### 5.3.2 Immune Subset Analysis

Peripheral blood mononuclear cells (PBMC) will be assessed using multiparameter flow cytometry for immune subsets including but not necessarily limited to CD8+ T-cells, CD4+Foxp3- T-cells, Tregs, Tex, Th1, Th2 and Th17+ CD4+ T-cells, monocyte subsets, MDSC subsets. Assessment will include functional markers, i.e. PD-1, Tim-3, CTLA-4, PD-L1, HLA-DR, Ki67 and/or CD40.

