#### 9.4.8 Exploratory Analyses

The exploratory objectives such as seeking to identify potential biomarkers or T-cell and B-cell clones in peripheral blood which are associated with response, will be assessed using descriptive statistics as well as non-parametric methods such as exact Wilcoxon rank sum tests. The analyses will be done without formal adjustment for multiple comparisons, but in the context of the number of tests performed.

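### Systemic steroid exposure can change between the blood samples being compared, but the exploratory immune-marker analyses do not take it into account and recording of dose changes is optional

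*Combined protocol and SAP*

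**What the plan says.** **Entry.** Section 2.1.2 allows systemic steroids up to 10 mg/day of dexamethasone or equivalent: "Patients receiving current systemic steroids must be on a stable steroid dose", unchanged for at least 7 days.

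**On treatment.** For these patients Section 4.2 says "the investigator should try to taper/discontinue dosing after initiation of therapy, if appropriate", with no timetable. It adds: "Other exceptions include the use of physiologic doses of corticosteroids and steroid use for acute issues". Outside the listed exceptions, systemic glucocorticoids are generally not allowed.

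**Immune toxicity.** The Section 3.3.2 table says, for pneumonitis and for colitis, "Administer corticosteroids (initial dose of 1-2 mg/kg prednisone or equivalent) followed by taper". The general instructions set the taper at four weeks or more.

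**Markers.** Section 1.1.3 lists as exploratory objectives the host immune response after pembrolizumab and biomarkers that predict response or toxicity. Section 5.3.2 states: "Peripheral blood mononuclear cells (PBMC) will be assessed using multiparameter flow cytometry for immune subsets". Section 1.2.7 names 6 weeks, 18 weeks, 1 year, 2 years and progression as blood time points. The Section 5.1 sample calendar adds a baseline draw.

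**Analysis.** Section 9.4.8 plans descriptive statistics and "non-parametric methods such as exact Wilcoxon rank sum tests". Sections 5 and 9 do not mention steroids, and Section 9.4.6 plans no subgroup analyses.

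**Recording.** Section 4.1 requires all concomitant medication to be recorded, but where a medication changes, "documentation of drug dosage, frequency, route, and date may also be included on the CRF".

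**The concern.** With no control arm, the host response to pembrolizumab can only be judged by comparing each patient's samples over time. The protocol encourages a change in an immune-active treatment over that same interval. Section 3.3.2 itself classes corticosteroids with immunosuppressive treatment, since it turns to other immunosuppressants when they fail. In a patient who tapers between baseline and week 6, a rise in a T-cell subset mixes steroid withdrawal with PD-1 blockade.

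Two further routes exist. If steroid use at entry differs between patients who later respond and those who do not, baseline markers can differ for that reason alone. Samples drawn during or after steroid treatment of an immune event reflect the steroid as well as the event.

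At stake is the interpretation of the correlative results: a steroid effect could be taken forward as a pharmacodynamic effect or a predictive marker. If dose and dates were not captured, nobody could check afterwards.

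**Working it through.** **Plan's own figures.** None is given for the marker analyses. The primary design figures reproduce and are not touched by this point: at least 14 of 20 responders gives power 0.913 at an 80% response rate (stated 91%), and at least 12 of 20 gives 0.887 at 70% (stated 88%).

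**Timing.** Cycles last 21 days (Section 3.2), so the post-cycle-2 draw falls at 2 × 21 = 42 days, or 6 weeks. A taper begun after the first dose can be under way or complete by then.

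**Recording gap.** Under Section 4.1, routine medication recording ends 30 days after the last dose, apart from SAEs and ECIs. A footnote to the Section 5.1 sample calendar continues study bloods in patients who stop for a reason other than progression and start no new treatment. This can include a patient stopped for immune toxicity who is still tapering.

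**PCNSL.** About 10 of the 20 patients in cohort 2 are meant to have PCNSL (Section 9.2). In Section 6.3.2, CR requires no corticosteroid, whereas CRu allows any dose and PR disregards it. Steroid status at assessment is thus tied by definition to response category, separating CR from CRu and PR. It does not by definition separate responders from non-responders.

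**Illustration 1: change from baseline.** All inputs are assumptions: marker SD 1 at each visit, within-patient correlation ρ, no drug effect, n = 20, 40% (8 patients) tapering, and a rise of d SD on tapering.

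- SD of the change = √(2(1 − ρ)): 1.41, 1.00 and 0.71 for ρ = 0, 0.5 and 0.75.
- Spurious mean rise = share × d: 0.4 × 0.5 = 0.2 SD, and 0.4 × 1 = 0.4 SD.

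Simulated rejection by a two-sided 5% signed-rank test:

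| ρ | d = 0.5 | d = 1 |
|---|---|---|
| 0 | 8–9% | 18–19% |
| 0.5 | 12% | 28–29% |
| 0.75 | 18% | 43–45% |

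With ρ = 0.5 and d = 1, 20% tapering gives 10%. Restricting the 40% case to the 20 − 8 = 12 patients with no steroid change returns the rate to about 4–5%.

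**Illustration 2: baseline marker, responders v non-responders.** Two-sided 5% exact rank-sum test, no true association, 1 SD steroid effect unless stated:

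| Share on steroid (responders v non-responders) | 12 v 8 patients | 26 v 14 patients |
|---|---|---|
| 50% v 50% | about 5% | about 5% |
| 20% v 40% | 6–7% | 7–9% |
| 20% v 60% | 11–12% | 18% |
| 20% v 60%, 1.5 SD | 18% | 31% |

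The 26 v 14 split adds the two illustrative results in Section 9.2 (14 + 12 v 6 + 8). The documents do not plan to pool the cohorts in this way.

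**The case against.** Several points against the concern are sound.

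- The analyses are exploratory, and the words *such as* in 9.4.8 leave stratified or restricted methods open. The only adjustment it declines is for multiplicity. A reader might infer that the plan rules out allowing for steroids, or that steroid effects will be reported as drug effects. The text supports neither: it is silent, so such a misreading is possible but not certain.
- Entry dose is capped and must be stable, on-study use is restricted, and tapering is only where appropriate. That week-6 blood is drawn on less steroid, or none, is a possibility and not a stated fact.
- A reader might infer that steroids given for an immune event create a false predictor of toxicity. They cannot alter samples drawn before the event. This part holds only for samples taken during or after that treatment; baseline samples are affected only through entry steroids.
- Medications are recorded and reviewed throughout treatment, and the PCNSL response table has a steroid column assessed at the same time points as the research bloods. Some steroid information will therefore exist. What is not guaranteed is the dose and date of a change.
- The rejection rates rest on invented inputs. The signed-rank test is not named in 9.4.8, and modest imbalance leaves the rank-sum test near nominal. Section 11.2 reports early closure to accrual, so 20 per cohort may not be reached. With 12 patients, 40% tapering, 1 SD and ρ = 0.5, the rate is 17–18%.
- Restricting to unchanged-dose pairs conditions on something that happens after treatment starts. Patients who improve may be the ones who taper, so the restriction can remove responders selectively. It should not be the main analysis.

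These points limit the weight of the concern. They do not supply the missing steroid data or a planned check.

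**Conclusion.** The point stands as a low-cost improvement to the exploratory analyses. Steroid exposure can differ between the samples and groups being compared, there is no control arm, and the plan neither commits to taking exposure into account nor guarantees the data to do so. Marker changes and differences can therefore partly reflect steroids.

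The size is unknown. The figure of about 9% to 45% against a nominal 5% holds for 20 patients, 40% tapering, a 0.5 to 1 SD effect, correlation 0 to 0.75 and no drug effect. With few patients tapering, or equal steroid use in the groups compared, error stays near nominal.

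A reader might go further and doubt the trial's efficacy or safety results. The documents do not support that: this point leaves the primary ORR, duration of response, PFS, EFS, OS and toxicity reporting unaffected.

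**What to change.** 1. **Section 4.1.** For systemic corticosteroids, change *may* to *will* for dose and dates, and record the current dose at every research blood draw, including draws after treatment stops. Where draws have already been made, abstract the dose from the medical record.
2. **Section 9.4.8.** Keep the all-patient analysis. Report baseline marker comparisons stratified by steroid use at baseline. Add a sensitivity analysis of change from baseline limited to patients on no steroid at either sample or on an unchanged dose, and state that this conditions on a post-treatment variable.
3. **Section 9.4.8, toxicity markers.** Assess prediction of toxicity only from samples drawn before the event and before steroids are started for it.

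The cost is one mandatory data field, some record abstraction and a few sentences of analysis text. The restricted comparisons will be smaller and less precise, for example 12 of 20 patients if 40% taper. No clinical rule or patient care changes.

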#### **4.3 OTHER CONSIDERATIONS**

##### **4.3.1 Diet**

Patients should maintain a normal diet unless modifications are required to manage an AE such as diarrhea, nausea or vomiting.

##### **4.3.2 Contraception**

Pembrolizumab may have adverse effects on a fetus in utero. Furthermore, it is not known if pembrolizumab has transient adverse effects on the composition of sperm.

For this trial, male patients will be considered to be of non-reproductive potential if they have azoospermia (whether due to having had a vasectomy or due to an underlying medical condition).

Female patients will be considered of non-reproductive potential if they are either:

1. Postmenopausal (defined as at least 12 months with no menses without an alternative medical cause; in women <45 years of age a high follicle stimulating hormone (FSH) level in the postmenopausal range may be used to confirm a post-menopausal state in women not using hormonal contraception or hormonal replacement therapy. In the absence of 12 months of amenorrhea, a single FSH measurement is insufficient.); **OR**
2. have had a hysterectomy and/or bilateral oophorectomy, bilateral salpingectomy or bilateral tubal ligation/occlusion, at least 6 weeks prior to screening; **OR**
3. has a congenital or acquired condition that prevents childbearing.

Female and male patients of reproductive potential must agree to avoid becoming pregnant or impregnating a partner, respectively, while receiving study drug and for 120 days after the last dose of study drug by complying with one of the following:

1. practice abstinence† from heterosexual activity; **OR**
2. use (or have their partner use) acceptable contraception during heterosexual activity.

##### **4.3.3 Acceptable methods of contraception are‡:**

###### **4.3.3.1 Single method**

Use of one of the following is acceptable:

- intrauterine device (IUD)
- vasectomy of a female subject's male partner
- contraceptive rod implanted into the skin

#### 4.3.3.2 Combination method

Requires use of two of the following:

- diaphragm with spermicide (cannot be used in conjunction with cervical cap/spermicide)
- cervical cap with spermicide (nulliparous women only)
- contraceptive sponge (nulliparous women only)
- male condom or female condom (cannot be used together)
- hormonal contraceptive: oral contraceptive pill (estrogen/progestin pill or progestin-only pill), contraceptive skin patch, vaginal contraceptive ring, or subcutaneous contraceptive injection

†Abstinence (relative to heterosexual activity) can be used as the sole method of contraception if it is consistently employed as the subject's preferred and usual lifestyle and if considered acceptable by local regulatory agencies and ERCs/IRBs. Periodic abstinence (e.g., calendar, ovulation, sympto-thermal, post-ovulation methods, etc.) and withdrawal are not acceptable methods of contraception.

‡If a contraceptive method listed above is restricted by local regulations/guidelines, then it does not qualify as an acceptable method of contraception for patients participating at sites in this country/region.

Patients should be informed that taking the study medication may involve unknown risks to the fetus (unborn baby) if pregnancy were to occur during the study. In order to participate in the study patients of childbearing potential must adhere to the contraception requirement (described above) from the day of study medication initiation (or 14 days prior to the initiation of study medication for oral contraception) throughout the study period up to 120 days after the last dose of trial therapy. If there is any question that a subject of childbearing potential will not reliably comply with the requirements for contraception, that subject should not be entered into the study.

#### 4.3.4 Use in Pregnancy

If a subject inadvertently becomes pregnant while on treatment with pembrolizumab, the subject will immediately be removed from the study treatment. The site will contact the subject at least monthly and document the subject's status until the pregnancy has been completed or terminated. The outcome of the pregnancy will be reported to Merck without delay and within 2 working days to Merck if the outcome is a serious adverse experience (e.g., death, abortion, congenital anomaly, or other disabling or life-threatening complication to the mother or newborn).

**The study investigator will make every effort to obtain permission to follow the outcome of the pregnancy and report the condition of the fetus or newborn to Merck. If a male subject impregnates his female partner the study personnel at the site must be informed immediately and the pregnancy reported to Merck and followed as described above and in Section 8.1.4.3.**

